**MRI-related risk management:**

Subjects will be prescreened for MRI safety and excluded, if they are pregnant/ breastfeeding or claustrophobic, or have metal in their bodies. Subjects who report that they cannot tolerate lying flat on their back for an hour during scanning will be excluded.

All people involved with the study must remove all metal from their clothing and all metal objects from their pockets. They will also walk through a detector designed to detect metal objects before they enter the magnet room. No metal can be brought into the magnet room at any time. Also, once the subject is in the magnet, the door to the room will be closed so that no one from outside accidentally goes near the magnet. Subjects will be watched closely throughout the MR study.

Some subjects may feel uncomfortable or anxious. If this happens to, they may ask to stop the study at any time and we will take them out of the MR scanner. On rare occasions, some subjects might feel dizzy, get an upset stomach, have a metallic taste or feel tingling sensations or muscle twitches. These sensations usually go away quickly, but we will ask the subjects to tell the research staff if they have them.

Subjects will be fitted with ear plugs to protect their ears. Subjects will be provided a cushion underneath their knees for comfort and to release back strain from lying flat. The heart rate and breathing of the subjects will be monitored continuously during scanning. Subjects will be observed by the members of the research team at all times and be able to communicate with them throughout scanning via the intercom. Subjects will be removed from the scanner at their request, or in the event of an emergency or adverse reaction.

**Safeguard for vulnerable populations:**

Women of childbearing potential will not be included, if they are pregnant or breastfeeding. Women who are 50 years of age and older or who have absence of menses for two years will not receive pregnancy tests. All other women will receive urine pregnancy test.

**Confidentiality:**

Hard copies of all medical information collected from study participants will be kept in a locked filing cabinet. Unique identifiers will be used to label all data. Electronic files will be maintained on password-protected research computers. The imaging data will be stored on secure and HIPAA compliant servers in the MRRC. All team members will use password-protected research computers. Strict standards of confidentiality will be upheld at all times.

12. **Data and Safety Monitoring Plan:** Include an appropriate Data and Safety Monitoring Plan (DSMP) based on the investigator's risk assessment stated below. (Note: the HIC will make the final determination of the risk to subjects.)

- a. What is the investigator's assessment of the overall risk level for subjects participating in this study? **Minimal risk**
- b. If children are involved, what is the investigator's assessment of the overall risk level for the children participating in this study? *Write here*
- c. Include an appropriate Data and Safety Monitoring Plan. Examples of DSMPs are available here <http://your.yale.edu/policies-procedures/forms/420-fr-01-data-and-safety-monitoring-plans-templates> for
  - i. Minimal risk
  - ii. Greater than minimal
- d. For multi-site studies for which the Yale PI serves as the lead investigator:
  - i. How will adverse events and unanticipated problems involving risks to subjects or others be reported, reviewed and managed? *Write here*
  - ii. What provisions are in place for management of interim results? *Write here*
  - iii. What will the multi-site process be for protocol modifications? *Write here*

13. **Statistical Considerations:** Describe the statistical analyses that support the study design.

**Statistical Analyses:**

Demographic and clinical data: Independent-sample t-tests will be performed to compare the baseline values between the PD-neurofeedback and PD-control groups ( $p < 0.05$ , two-tailed).

**Aim 1:** A 2x2 mixed ANOVA with an interaction term will be performed to assess group differences in right insula-dmFC functional connectivity (between-subject factor: group, within-subject factor: right insula-dmFC functional connectivity during the first and last control scan, interaction: group x insula-dmFC functional connectivity). Post-hoc tests will be Bonferroni-corrected,  $p < 0.05$ .

**Aim 2:** Within-group one-sample t-tests will be performed on the right insula and dmFC resting-state functional connectivity maps. A 2x2 mixed ANOVA with an interaction term will be performed to assess group differences in resting-state functional connectivity (between-subject factor: group, within-subject factor: resting-state functional connectivity pre- and post-intervention, interaction: group x resting-state functional connectivity). All group analyses will be corrected for multiple comparisons using the false discovery rate procedure ( $p < 0.05$ , two-tailed) (Genovese et al., 2002).

**Aim 3:** The scores (i.e., time required for completion) of the motor function tests will be z-transformed and summed to obtain a composite motor function score for each subject. A 2x2 mixed ANOVA will be performed to compare the differences in motor functioning between the groups pre- and post-training (between-subject factor: group, within-subject factors: MDS-UPDRS motor exam and composite motor function scores, interaction: group x motor assessment). Post-hoc tests will be Bonferroni-corrected,  $p < 0.05$ .

**Exploratory Aims:** A paired-sample t-test will be performed to assess the differences in the whole-brain functional connectivity associated with the imagery and video-watching tasks. The results will be corrected for multiple comparisons using the false discovery rate procedure ( $p < 0.05$ , two-tailed) (Genovese et al., 2002).

**Power analysis:** The sample size calculation is based on the clinically important difference (CID) in the primary motor outcome measure. Approximately a 5-point decrease in the mean MDS-UPDRS motor exam score after an intervention has been defined as a moderate CID (Schrag et al., 2006; Shulman et al., 2010). In this study, we expect a moderate CID. We used the mean and standard deviation of the MDS-UPDRS motor exam scores ( $24 \pm 9$ ) of a large group of subjects with PD (N = 347) as the population mean and standard deviation (Shulman et al., 2010). Assuming  $\alpha = 0.05$  and power = 0.80, 22 subjects are required for a moderate CID. Considering the possibility of a 35% drop-out rate between Visits 1 and 4, we will plan to recruit 30 subjects each for the PD-neurofeedback and PD-control group, total of 60 subjects. We will also perform an adaptive interim statistical analysis based on the primary motor outcome (Bauer and Kohne, 1994). If the p values fall between 0.023 (efficacy boundary) and 0.5 (futility boundary), then we will recalculate the sample size based on conditional power (e.g., 0.80). If the p value is  $< 0.023$  (i.e., significant difference) or  $> 0.5$  (i.e., no hope to find a significant difference), we will terminate the study.

**Randomization:** Group assignment of subjects will be determined by the end of Visit 1. We will use a covariate adaptive randomization method (Lin et al., 2015). Age and gender are important variables and need to be controlled during randomization. This method will take into account age and gender and sequentially assign each new subject accordingly. This approach will allow us to balance the two groups in terms of age and gender.

**Potential problems:** 1) Variability in neurofeedback learning will be expected. We aim to reduce variability by providing personalized and detailed motor imagery scripts and facilitate learning with homework. 2) In general, attrition rate can be an issue especially in control groups. Our active control design will help minimize this by controlling for subject engagement in tasks during visits and at home, and for time spent with research staff.

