**Aim 3: To examine the effects of neurofeedback-guided motor imagery training on motor function.**

We will measure the severity of motor dysfunction using clinical rating scales and administer standard motor function tests (e.g., timed up and go, five times sitting-to-standing) to measure movement speed and vigor in PD-neurofeedback and PD-control groups. These measurements will be performed at baseline and post-training. *Hypothesis: There will be significant improvement in motor function in the PD-neurofeedback compared with the PD-control group post-training.*

This project has potential for direct clinical significance for patients with PD: 1) Interventions such as deep brain stimulation exert their effect by altering the abnormal activity of targeted brain circuits underlying PD pathology. fMRI-based neurofeedback training offers an unprecedented opportunity to have a similar effect noninvasively. 2) The mental strategies that were successfully and reliably used during neurofeedback could be practiced off-line. Therefore, neurofeedback has the potential to be implemented as a personalized treatment modality. 3) It could also be incorporated into rehabilitation and exercise programs as an adjunct treatment modality.

**Rationale for Additional fMRI Experiments:** 1) Our findings have shown that despite engaging different brain networks specific to imagery type (i.e., motor versus visual), subjects in both PD-neurofeedback and PD-control groups improved their motor function comparably (Tinaz et al., 2022). This suggests that there may be a "shared" brain network subserving both motor and visual imagery and mediating the motor response. To test this hypothesis further, we plan on using a hybrid mental imagery of everyday task performance in the scanner that will include both motor and visual features. The results of this experiment will also inform the choice of off-line imagery practice that can potentially yield most benefits. 2) It is also important to establish to what extent mental imagery of everyday task performance is equivalent to observation of the actual task performance in terms of brain networks. If the brain networks involved in these tasks overlap significantly, this will further support the use of mental imagery as a mental training tool.

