## 2.4. Research Visit 1:

### 2.4.1. Clinical Evaluation:

All subjects will be asked to temporarily hold the morning dose of their dopaminergic medication on Visit 1. Upon obtaining informed consent to participate in the study, [name] will perform an initial physical and neurological examination on all subjects. The diagnosis of idiopathic PD will be made according to the UK Brain Bank diagnostic criteria (Hughes et al., 1992). Cognitive and emotional problems may interfere with imagery performance. To rule out dementia and depression, the Montreal Cognitive Assessment test and Beck Depression Inventory-II will be administered, respectively (Nasreddine et al., 2005; Beck 1997). The Movement Disorders Society-Unified Parkinson’s Disease Rating Scale (MDS-UPDRS) (Goetz et al., 2008) and Hoehn & Yahr staging (Hoehn and Yahr, 1998) are standardized clinical rating scales to determine disease severity and stage in PD. Part III of the MDS-UPDRS is the objective motor examination part that also includes Hoehn & Yahr staging. This part will be videotaped for all subjects. The videos will be viewed and exam features scored by another neurologist with movement disorders training ([name]) who is blind to subjects’ group assignment. The standardized motor function tests (timed up and go, 10-m walking, 2-min endurance walking, five

times sit-to-stand, turning in place 360 degrees, and Physical Performance Test) will be administered to measure movement speed and vigor. All of these are standardized tests and scales, and are commonly used in clinical practice to assess symptom severity in PD.

Immediately after this initial assessment, subjects will take their dopaminergic medication. Subsequently, subjects will be administered additional self-evaluation questionnaires. These include: Starkstein Apathy Scale (Starkstein et al., 1992), Spielberger State-Trait Anxiety Inventory (Spielberger et al., 1982), Parkinson disease Fatigue Scale (Brown et al., 2005), Parkinson disease quality of life scale (PDQ39) (Peto et al., 1995), Self-Assessment Parkinson's Disease Disability Scale (SPDDS) (Biemans, et al., 2001) and Multidimensional Assessment of Interoceptive Awareness (MAIA) questionnaire (Mehling et al, 2012). Motor imagery skills will be tested using the Movement Imagery Questionnaire-3 (MIQ-3) (Williams et al., 2012).

After visit 1, subjects will be randomized to PD-neurofeedback and PD-control groups (see 13. Statistical Considerations).

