#### **2.7.1. Clinical Evaluation:**

The MDS-UPDRS part III motor examination and the standardized motor function tests will be repeated for all subjects. The MDS-UPDRS part III will be videotaped and the videos will be scored by a neurologist with movement disorders training ([name]), who is blind to subjects' group assignment.

Immediately after this final assessment, subjects will take their dopaminergic medication.

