The proposed research plan involves a neurological examination, administration of questionnaires and paper-pencil tests, behavioral testing, and MRI. Subjects who are on dopaminergic medications (e.g., carbidopa/levodopa, dopamine receptor agonists) will be asked to hold the first morning dose of medications temporarily for research visits 1 and 4. Only patients who would be safely able and willing to comply with this requirement will be enrolled. Immediately upon completion of testing, subjects will resume their routine medication schedule. If at any point of testing the subjects experience discomfort as a result of being off their medication, the testing will be terminated and they will be given their medication. Subjects will always be scanned after they take their dopaminergic medications. The potential risks associated with individual study procedures are as follows:

Clinical Evaluation:

The clinical evaluation including neurological examination, questionnaires, and paper-pencil tests does not entail any medical risk. Subjects may choose to stop participating in the surveys/questionnaires at any time.

MRI in 3 Tesla scanner:

Subjects are at risk for injury from the scanner, if they have metal objects in their bodies (e.g., pacemakers, aneurysm clips, metallic prostheses, implanted delivery pumps, cochlear implants, shrapnel fragments). Welders and metalworkers are also at risk for injury because of possible presence of small metal fragments in the eye, of which they may be unaware. Individuals with fear of confined spaces (i.e., claustrophobia) may become anxious during MRI. The scanner makes a thumping noise created by the radiofrequency waves necessary for forming the images. The noise can be loud enough to damage hearing. Lying flat in the scanner for an hour might cause discomfort for some subjects. On rare occasions, some people might feel dizzy, get an upset stomach, have a metallic taste or feel tingling sensations or muscle twitches. These sensations usually go away quickly.

11. **Minimizing Risks:** Describe the manner in which the above-mentioned risks will be minimized.

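### The Aim 3 composite scores every motor function test as completion time, which gives no usable z-score for the fixed-duration 2-minute walk and leaves the Physical Performance Test undefined

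*Combined protocol and SAP*

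**What the plan says.** Section I, item 13 (Statistical Considerations, Aim 3) gives one scoring rule for the whole battery: "The scores (i.e., time required for completion) of the motor function tests will be z-transformed and summed to obtain a composite motor function score". No test is exempted, no sign is reversed, and the mean and SD used for the z-scores are not named.

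Section 2.4.1 applies the same label to six tests: "The standardized motor function tests (timed up and go, 10-m walking, 2-min endurance walking, five" and, continuing over the page break, "times sit-to-stand, turning in place 360 degrees, and Physical Performance Test) will be administered to measure movement speed and vigor". Section 2.7.1 says of Visit 4 that "the standardized motor function tests will be repeated for all subjects". The Physical Performance Test appears only in the Section 2.4.1 list, without a score. Distance is not mentioned as the result of the walk.

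The composite then enters the Aim 3 mixed ANOVA together with the clinical rating: "within-subject factors: MDS-UPDRS motor exam and composite motor function scores, interaction: group x motor assessment".

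**The concern.** Completion time suits a task with a fixed amount of work, such as rising from a chair five times. The 2-minute walk fixes the time and lets the amount of work vary, so its completion time carries no information about performance. A rule that requires a z-score of that time fails. The Physical Performance Test cannot be placed in the sum either, because its metric and direction are not given.

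The composite is one of the two motor measures in the Aim 3 analysis. As the plan stands, the analyst must decide which tests enter, in what unit, in which direction and against which reference distribution. None of these choices is recorded in advance.

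**Working it through.** The plan gives no SD, effect size or power for the composite, so there is no stated figure to reproduce. The check applies the rule as written and then looks at the repairs open to an analyst.

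**1. The walk under the stated rule.** The duration, 2 min = 120 s, comes from the name of the test.
- Each finisher has x = 120, so the mean is 120 and the SD is 0.
- z = (120 - 120)/0, which is undefined at any sample size.
- A subject who stops early has no completion time and so adds no spread. The SD stays 0 however many stop.
- A sum with an undefined term is undefined, so the six-test composite does not exist for any subject.

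**2. If stop time were entered instead (an assumption, not the plan's rule).** With n subjects, of whom k stop at one common time, and the sample SD:
- z(stopper) = -sqrt[(n - k)(n - 1)/(nk)].
- For n = 60 and k = 1 this is -sqrt(59 x 59/60) = -7.62, whatever the stop time. Each finisher gets sqrt[1 x 59/(60 x 59)] = +0.13.
- With two stoppers among 60, at 20 s and 119 s, the mean is 118.32 and the SD 12.91. The z-scores are -7.62 and +0.05.

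On timed tests lower is better, so under this substitution an early stop could be scored as a very good result. The size depends heavily on how many stop and when, and the documents give neither.

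**3. Repairs to the walk and the Physical Performance Test.** Assume an equal standardised effect e on every test and a common inter-test correlation r once all tests point the same way. For m aligned tests the composite effect is e x m/sqrt[m + m(m - 1)r]. For six tests with one left unreversed it is e x 4/sqrt(6 + 10r).

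| Composite | r = 0.3 | r = 0.5 | r = 0.7 |
|---|---|---|---|
| Six tests, all aligned | 6/sqrt(15) = 1.549 | 6/sqrt(21) = 1.309 | 6/sqrt(27) = 1.155 |
| Six tests, distance unreversed | 4/sqrt(9) = 1.333 | 4/sqrt(11) = 1.206 | 4/sqrt(13) = 1.109 |
| Ratio to aligned | 0.861 | 0.921 | 0.961 |
| Five tests (walk out), ratio | 0.973 | 0.986 | 0.993 |
| Four tests (walk and Physical Performance Test out), ratio | 0.937 | 0.966 | 0.984 |

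Effects are in units of e. They describe the composite alone and not the joint ANOVA with the MDS-UPDRS.

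**4. The reference for the z-scores.** Take a true group difference in change of -0.50 Visit 1 SD, equal group means at Visit 1, equal group sizes, and a Visit 4/Visit 1 within-group SD ratio q.
- Visit 1 reference: -0.50/1 = -0.50 for any q.
- Each visit standardised on its own pooled SD: the Visit 4 SD is sqrt(q² + 0.25²). For q = 0.8 this is 0.838, giving -0.50/0.838 = -0.60. For q = 1.25 it is 1.275, giving -0.50/1.275 = -0.39.
- Standardised within group and visit: every group mean is 0 at each visit, so the contrast is exactly 0.

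The plan does not exclude any of the three.

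**The case against.** **The investigators meant distance, or only the timed tests.** Either is plausible. The Aim 3 text in the Statement of Purpose describes the plan to "administer standard motor function tests (e.g., timed up and go, five times sitting-to-standing) to measure movement speed and vigor", and both of its examples are timed. They are only examples, however, and nothing removes the walk from the composite. Distance would still need its sign reversed, which the plan does not say. The charitable readings therefore need a written rule too.

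**The fault shows itself and is cheap.** An SD of 0 is seen at once and cannot quietly bias a result, and leaving the walk out costs little. This stands, and it limits the consequence. It does not settle which repair will be chosen.

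**Stopping early would count as better.** A reader might infer this, because both batteries are done with the morning dose held and item 10 (Risks) says: "If at any point of testing the subjects experience discomfort as a result of being off their medication, the testing will be terminated". The documents do not support it as a result of the stated rule. A subject who stops has no completion time, and terminating the session would leave later tests missing as well. Section 2.2 also screens out people for whom being off medication is unsafe, and no stopping rate is given. The figures in step 2 hold only if stop time is substituted.

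**Motor results already reported may be affected.** The rationale for the additional experiments says that "subjects in both PD-neurofeedback and PD-control groups improved their motor function comparably". It does not say how those results were scored, so nothing about them can be concluded here.

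**Conclusion.** The point holds as an error in a stated rule. Applied as written, completion time gives an SD of 0 for the 2-minute walk, and the six-test composite cannot be computed. This needs no assumption beyond the fixed duration of the walk. The Physical Performance Test score and the z-score reference are also unspecified, and the choice of reference can distort the group-by-time contrast or remove it.

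The loss from an unaligned distance score is moderate: 86-96% of the composite effect is kept, given equal effects and r from 0.3 to 0.7.

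A reader might infer that the trial's sizing or its early-stopping decision is compromised. It is not on this account: item 13 bases both on the primary motor outcome, the MDS-UPDRS motor exam. The consequence is confined to the Aim 3 composite and what is concluded from it.

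**What to change.** In item 13, Aim 3:
- List the tests that enter the composite and apply completion time only to those that are timed.
- Enter the 2-minute walk as distance multiplied by -1, or exclude it if distance is not recorded.
- State the score of the Physical Performance Test and align it so that lower means better throughout, or exclude it.
- State how a test that was not finished is handled in the analysis. Reversed distance alone does not settle this, since a fast walker who stops late may cover more ground than a slow finisher.
- Standardise both visits with the pooled Visit 1 mean and SD of all randomised subjects. This preserves the group-by-time contrast and keeps change shared by both groups visible.

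The cost is wording only if walking distance is already recorded, which the documents do not say. Otherwise it is one case report form field at Visits 1 and 4, or the exclusion. Under the step 3 assumptions, excluding the walk keeps 97-99% of the composite effect, and excluding both doubtful tests keeps 94-98%.

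### Aim 3 names the two motor instruments, not time, as within-subject factors, and the group-by-time test it probably intends adjusts for neither baseline score nor age and gender

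*Combined protocol and SAP*

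**What the plan says.** Section I, 13, Aim 3 states its purpose as being to "compare the differences in motor functioning between the groups pre- and post-training". The model in the parenthesis that follows has group as the between-subject factor and "within-subject factors: MDS-UPDRS motor exam and composite motor function scores, interaction: group x motor assessment". Time is not a listed term.

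The two preceding paragraphs do attach time to the factor. Aim 1 has "within-subject factor: right insula-dmFC functional connectivity during the first and last control scan" and Aim 2 has "within-subject factor: resting-state functional connectivity pre- and post-intervention".

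The Aim 3 hypothesis in Section I, 1 is that "There will be significant improvement in motor function in the PD-neurofeedback compared with the PD-control group post-training".

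The data for an adjusted analysis are planned. At Visit 1 (2.4.1) the MDS-UPDRS part III is examined before allocation: "This part will be videotaped for all subjects", with scoring by a neurologist blind to group. At Visit 4 (2.7.1), "The MDS-UPDRS part III motor examination and the standardized motor function tests will be repeated for all subjects".

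Under Randomization, "Age and gender are important variables and need to be controlled during randomization". No analysis in Section 13 carries a baseline score, age or gender as a covariate.

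**The concern.** The sentence does not define one model. Group, time and two instruments would make a 2x2x2 design, so the 2x2 label fits either group by instrument (the literal text) or group by time run once per outcome (the probable intent). Only the second tests the Aim 3 hypothesis. The first asks whether the group gap differs between a raw-point scale and a sum of z-scores.

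On the probable reading, the interaction test is equivalent to an unadjusted two-sample t-test on change. It uses the Visit 1 score less efficiently than a covariate would, and it ignores two variables that the plan calls important and builds into allocation. The loss matters most if the 35% drop-out that the plan allows for occurs.

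The choice of model also affects trial conduct. The Power analysis paragraph stops or resizes the trial according to one interim p-value for the primary motor outcome (limits 0.023 and 0.5), and nothing states which model produces it.

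**Working it through.** **Inputs from the plan (Section 13, Power analysis).** Difference 5 points, SD 9, alpha 0.05, power 0.80, 22 subjects required, 35% drop-out, 30 recruited per arm. If the drop-out occurs, 30 × 0.65 = 19.5, or about 20 completers per arm.

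**Assumed, because the documents are silent.** Two-sided testing; the Visit 1 to Visit 4 correlation ρ (0.3 to 0.9); and the share of residual variance that age and gender explain.

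**The plan's own figures.** The 22 is reproduced only by a single-group, one-sided t-test with difference 5 and SD 9 (n = 22, power 0.809). A two-group, two-sided t-test on one score with SD 9 needs 52 per arm. The 30 is 22 × 1.35 = 29.7. So the 22 was not derived from the Aim 3 between-group contrast and does not establish ρ. If it is nevertheless read as 22 per arm on change scores, it implies ρ of about 0.79 (SD of change about 5.8).

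**Change score against baseline-adjusted ANCOVA.**
- Change score: residual SD 9√(2(1−ρ)), df 2n−2.
- ANCOVA: residual SD 9√(1−ρ²), df 2n−3.
- Variance ratio: (1−ρ²)/(2(1−ρ)) = (1+ρ)/2.
- Example at ρ = 0.7: 9√0.6 = 6.97 against 9√0.51 = 6.43, ratio 0.85.

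Power from the noncentral t, change score / ANCOVA:

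| ρ | 20 per arm | 30 per arm | Completers per arm for 80% |
|---|---|---|---|
| 0.5 | 0.402 / 0.506 | 0.562 / 0.685 | 52 / 40 |
| 0.7 | 0.599 / 0.669 | 0.780 / 0.842 | 32 / 27 |
| 0.8 | 0.772 / 0.814 | 0.917 / 0.941 | 22 / 20 |
| 0.9 | 0.969 / 0.975 | 0.997 / 0.998 | 12 / 11 |

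At ρ = 0.3 and 20 per arm the figures are 0.304 and 0.434. All of these are fixed-sample values; the plan's sample-size recalculation is not modelled.

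**Adding age and gender.** Simulation, 25,000 runs per setting: 60 subjects, biased-coin minimisation (0.85) on age tertile and gender, 38 of 60 male as in the Planned Enrollment table, random 35% drop-out (mean 19.8 completers per arm). Power for change score / baseline ANCOVA / ANCOVA with age and gender:

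| ρ | Age and gender explain nothing | They explain 10% of residual variance |
|---|---|---|
| 0.5 | 0.405 / 0.497 / 0.487 | 0.395 / 0.485 / 0.520 |
| 0.7 | 0.596 / 0.656 / 0.641 | 0.596 / 0.654 / 0.682 |
| 0.8 | 0.774 / 0.805 / 0.794 | 0.772 / 0.803 / 0.826 |
| 0.9 | 0.966 / 0.969 / 0.964 | 0.972 / 0.975 / 0.980 |

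If the two covariates are uninformative, including them costs 0.005 to 0.015 of power (for example 0.656 − 0.641 = 0.015 at ρ = 0.7). Type I error in the 10% setting, in the same order, was 0.046 / 0.045 / 0.048 at ρ = 0.5 and 0.045 / 0.046 / 0.052 at ρ = 0.8.

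A second simulation (44 subjects, ρ = 0.7, 6,000 null runs) took stronger covariates. With 20% and 30% of residual variance explained, the unadjusted test's type I error fell to 0.032 and 0.025, while the fully adjusted model gave 0.045 and 0.050. Omitting the allocation variables therefore makes the test conservative, not liberal.

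**The literal group-by-instrument test.** Take 22 per arm, a post-training benefit of 5/9 = 0.556 SD on both instruments, and instrument correlation 0.5, averaging over visits. With composite SD s, the interaction effect is (5 − (5/9)s)/2 and its SD is √((1+ρ)/2) × √(81 + s² − 9s).
- s = 9 (equal scales): effect zero, rejection 0.050.
- s = √(6 + 30 × 0.5) = 4.58 (six z-scores correlated 0.5): 0.091 at ρ = 0.5 and 0.084 at ρ = 0.8.
- s = √6 = 2.45 (six uncorrelated z-scores): 0.135 and 0.120.

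Run as written, the test would almost never detect the hypothesised benefit.

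**The case against.** The strongest reply has four parts.

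- **Time is in the sentence.** The purpose clause compares the groups before and after training, and Aims 1 and 2 use the same shorthand, so nobody is likely to run group by instrument. This is fair. The literal-reading figures show only why the wording needs correcting, and the case does not rest on them.
- **Group by time is valid, and the gain from ANCOVA depends on an unknown ρ.** Both points stand. The closed form also flatters ANCOVA by about 0.01, because it ignores chance baseline imbalance: the simulation gives 0.497, 0.656 and 0.805 where the formula gives 0.506, 0.669 and 0.814. At ρ = 0.8 the simulated gain from baseline is 0.805 − 0.774 = 0.031, and 0.794 − 0.774 = 0.020 if age and gender are added and explain nothing.
- **Age and gender are already handled at allocation.** Leaving them out does not inflate the error rate, and the 10% share is illustrative. That stands. The argument for including them is precision, and correct size if they turn out to be strongly prognostic.
- **The primary model would change after results are known.** Section I, 1 (Rationale for Additional fMRI Experiments) reports that motor function improved to a similar degree in both arms. This is a real cost, and disclosure does not remove it entirely. But the sentence has to be rewritten after those results in any case, and continuing to report group by time lets readers see whether the choice of model matters.

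**Conclusion.** The concern holds as a matter that should be fixed, with medium confidence. The Aim 3 factor list is wrong for its hypothesis, and the probable intended test leaves out covariates that are already collected. The consequence is lost precision, not bias.

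Against the change score, at about 20 completers per arm, the simulated gain from full adjustment runs from 0.08 (0.487 − 0.405, covariates null) to 0.125 (0.520 − 0.395, covariates explaining 10%) at ρ = 0.5. It is 0.045 to 0.086 at ρ = 0.7, 0.020 to 0.054 at 0.8, and essentially nil at 0.9. These sizes rest on an assumed ρ, random drop-out, SD 9 at both visits and a 5-point between-group difference. Two parts of the finding depend on none of these: the factor list needs correcting, and the model behind the interim p-value needs naming.

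**What to change.** Replace the Aim 3 model with one model per outcome.

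- **Primary:** ANCOVA of the Visit 4 blinded-video MDS-UPDRS part III score on group, Visit 1 score, age and gender, reporting the adjusted group difference with a 95% CI.
- **Secondary:** the same model for the composite motor score.
- **Interim:** state that the p-value compared with 0.023 and 0.5 comes from the primary model.
- **Sensitivity:** report the group-by-time ANOVA for each outcome, with time (Visit 1, Visit 4) named as the within-subject factor.

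The cost is a dated amendment to the analysis plan. No new data are needed, since Visit 1 scores, age and gender are already collected. The amendment must disclose that it follows the comparative motor results described in Section I, 1. The statistical price is 0.005 to 0.015 of power if age and gender explain nothing.
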